#### Interpretation and assumption of quantitative data

The quantitative assessment of nasal deposition, retention and clearance will be determined as a percentage of total nasal deposition (quantified using the first planar image immediately after inhalation of the radioaerosol) as a function of intensity within defined areas of the nasal cavity, left and right of the maxillary, frontal, ethmoidal and sphenoidal sinuses using standard protocol as briefly described below. Count rates in the selected region of interests will be analysed using the MATLAB Software or ImageJ Software packages (<http://rsb.info.nih.gov/ij/>). Count rates will be corrected for background activity and radioactive decay.

For analysis of the distribution of the radiolabelled saline into the different compartments, all serial images will be superimposed with regions of interest (ROI) of the nasal airways and sinuses defined as shown in Figures 6 and 7. The activity is obtained in these ROIs.

[figure not shown]

Figure 6. Regions of interest of the nasal cavity of the right and left maxillary and frontal sinuses (MR, FR, FL and ML). Image was taken from [9].

The primary endpoint of this study is the total area of distribution ( $\text{mm}^2$ ) of radiolabelled saline immediately after administration by the NMM ( $T_0$ ). This will be evaluated for each of subsites (surgically expanded ostia of the paranasal sinuses and oropharynx) and compared between treatments (A-D) which correspond to the different pulse frequencies tested. Between-treatment differences in total area of deposition of radiolabelled saline at each subsite will be compared by means of one-way analysis of variance (ANOVA) with application method as a factor.

Pairwise comparisons will be performed between each of the pulsed application methods and the continuous application (no pulse). Pairwise comparisons will be tested using a two-tailed p-value of  $<0.05$ .

Clearance will be calculated by the decrement in total radiolabelled saline between  $T_0$ ,  $T_{20}$  and  $T_{60}$ . Clearance will be evaluated for each subsite and compared between treatments (A-D). As with the primary efficacy endpoint, between-treatment differences in radiolabelled clearance will be tested by means of one-way analysis of variance (ANOVA) with application method as a factor. Pair-wise comparisons will be made between each of the pulsed application methods and the continuous application (no pulse).

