The retention of radiolabelled saline will be evaluated as the Area Under the Curve between  $T_0$  and  $T_{60}$  ( $\text{AUC}_{0-60}$ ) of the following assessments:

- the total area of deposition of radiolabelled saline
- the intensity of radiolabelled saline

The AUCs will be evaluated for each subsite and compared between treatments (A-D). Between-treatment differences in AUCs will be tested by means of one-way analysis of covariance (ANCOVA) with application method as a factor and the value at  $T_0$  as

covariate. Pair-wise comparisons will be made between each of the pulsed application methods and the continuous application (no pulse).

[figure not shown]

Figure 7. Example of superposition of anterior gamma camera images of radiolabelled aerosol after nasal delivery [9]. After deletion of the activity in the central nasal cavity, the aerosol penetration into the sinuses will be highlighted in B and D.

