## 4.0 Study design

### 4.1 Type of study

This is a single centre, randomised, controlled, cross-over clinical study investigating the deposition of aerosols generated by the NMN prototype into the nasal cavity using different pulse frequencies.

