#### **4.3 Number of participants**

Employing a cross-over design enables each participant to act as its own control, and reduces the overall number of patients needed to assess aerosol deposition.

For this investigational study, participants who meet all the eligibility criteria will be enrolled and randomised into the study until 11 participants who complete the study are met.

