## 6.0 Trial procedure

### 6.1 Research plan

The study will have a cross-over design with each participant completing 4 different device settings over a period of 4 visits with at least a 72 hour wash-out period in between visits.

[figure not shown]
In the first visit, participants will sign a written informed consent, undergo lung function, urinary cotinine and skin prick tests, as well as completing 2 standard and validated clinical questionnaires: Woolcock's Clinical questionnaire and SinoNasal Outcome Test (SNOT) 22 [20] on medication use, medical history and smoking history. Participants will then undergo a full head high-resolution CT scan of the upper respiratory tract before being subjected to 1 of 4 randomised treatments of radio-labelled saline by using the NMN: A) no pulse frequency (continuous delivery mode), B) 10 Hz pulse frequency, C) at 50 Hz pulse frequency, or D) at 100 Hz pulse frequency. Immediately following administration of the radio-labelled aerosol, deposition of aerosols will be measured via gamma camera and dynamic SPECT/PET images for the first 20 minutes and finally at 1 hour to assess deposition, retention and clearance.

[figure not shown]
In subsequent visits (2-4), participants undergo a brief medical interview as well as repeating the urinary cotinine tests to confirm non-smoking status before further administration of radio-labelled aerosol via one of the four treatment processes as defined by the randomisation sequence.

Prior to the initiation of the screening assessments, potential participants will be given a complete explanation of the study.

Once an individual has agreed to participate and signed a copy of the Informed Consent documents, information will be obtained from the participant to determine their eligibility for enrolment in the study

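### Section 3.4 analyses a four-visit cross-over with one-way ANOVA/ANCOVA and no participant term, so with positive within-participant correlation the ANOVA is conservative and loses power

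*Protocol*

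**What the plan says.** Protocol Section 4.1 describes the trial in these words: "This is a single centre, randomised, controlled, cross-over clinical study". Section 6.1 has "each participant completing 4 different device settings over a period of 4 visits". Section 4.3 gives the reason for the design: "Employing a cross-over design enables each participant to act as its own control". It adds that this lowers the number of people needed, and sets enrolment to continue until 11 have completed.

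Section 3.4, under Interpretation and assumption of quantitative data, then fixes three analyses:

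- **Area at T0 (primary endpoint), by subsite:** differences "will be compared by means of one-way analysis of variance (ANOVA) with application method as a factor".
- **Clearance, by subsite:** "between-treatment differences in radiolabelled clearance will be tested by means of one-way analysis of variance (ANOVA) with application method as a factor".
- **Retention (AUC from T0 to T60), by subsite:** differences "will be tested by means of one-way analysis of covariance (ANCOVA) with application method as a factor", with the T0 value as covariate.

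Each is followed by three pairwise comparisons of a pulsed setting with continuous delivery. For the primary endpoint these are two-tailed at 0.05. The text does not say whether the pairwise tests are paired. No participant, period or sequence term appears in the protocol, and no repeated-measures or mixed model.

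**The concern.** A one-way ANOVA with application method as its only factor is a model for four independent groups. Applied here, it takes 11 participants at 4 visits as 44 independent observations. Stable differences between participants, such as nasal and sinus anatomy, are common to all four of a person's visits. They cancel when settings are compared within a person, but the one-way model counts them as noise.

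The analysis therefore does not deliver the advantage that Section 4.3 uses to justify the small sample. Section 3.2 makes the choice of an optimal frequency the main objective, and Section 2.3 says the results are intended to support registration of the device. With 10 or 11 participants there is little power to spare, and a real frequency effect could be reported as no difference.

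**Working it through.** **Inputs from the protocol.** Four settings, one per visit (4.2, 6.1); 11 completers (4.3), with a stated minimum of 10 (5.1); two-tailed 0.05 for pairwise tests (3.4); application method as the only factor (3.4).

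**The plan's own figure.** The sample size cannot be reproduced. The protocol gives no effect size, standard deviation, correlation or power, and refers only to two earlier studies of five subjects each.

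**Assumptions.** Normal data, total standard deviation (SD) 1, and equal correlation ρ between any two visits of one person. The protocol does not give ρ, so a range is shown.

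**Step 1: degrees of freedom.** One-way error: 44 − 4 = 40. With a participant term: 40 − 10 = 30.

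**Step 2: standard error of a difference between two settings.**

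- The one-way error mean square estimates the total variance, so the planned SE is √(2/11) = 0.426 SD.
- The true SE is √(2(1 − ρ)/11), which is 0.357 / 0.302 / 0.234 SD at ρ = 0.3 / 0.5 / 0.7.
- The ratio is 1/√(1 − ρ) = 1.20 / 1.41 / 1.83.

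**Step 3: true size and power, by simulation** (n = 11, 400,000 trials per setting). The one-way error term (40 df) is compared with the participant-adjusted one (30 df). For power, the D-versus-A difference is set so that the adjusted contrast has 80%.

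| ρ | Size of one-way F | Size of contrast, one-way error | Difference used (SD) | Power, one-way error | Power, participant term |
|---|---|---|---|---|---|
| 0 | 5.0% | 5.0% | 1.24 | 81% | 80% |
| 0.1 | 3.5% | 4.0% | 1.17 | 77% | 80% |
| 0.2 | 2.4% | 2.9% | 1.10 | 74% | 80% |
| 0.3 | 1.5% | 2.1% | 1.03 | 68% | 80% |
| 0.5 | 0.4% | 0.9% | 0.87 | 52% | 80% |
| 0.7 | 0.05% | 0.2% | 0.68 | 27% | 80% |

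With the participant term, the F test and the contrast both hold about 5% at every ρ. With n = 10 the pattern is the same (F test 1.5% / 0.4% / 0.07% at ρ = 0.3 / 0.5 / 0.7).

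**Step 4: hand check at ρ = 0.5.** The one-way contrast is significant when the observed difference exceeds 2.021 × 0.426 = 0.862 SD. The true difference is 0.873 SD with true SE 0.302. Power is therefore about P(Z > (0.862 − 0.873)/0.302) = P(Z > −0.04), or about 52%, in agreement with the table.

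**Step 5: the AUC ANCOVA.** The table does not carry over to it, because the T0 covariate may absorb participant variation. An illustrative check took the AUC as 0.8 × T0 plus noise, with T0 correlated 0.5 or 0.7 across visits. Pairwise size was about 5% when no participant variation remained after T0, and about 1% when half the residual variance was between participants.

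**The case against.** Several points on the other side are sound.

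- **The pairwise tests may be paired.** Section 3.4 does not say. Run as paired t-tests (10 df) they would hold 5% size and have about 74% power at every correlation. The pairwise losses above therefore apply only if the tests use the one-way error term. This does not rescue the ANOVA itself, whose factor is named.
- **The correlation is not given.** At zero nothing is lost, and at 0.1 or 0.2 the loss is small. But the reason for the cross-over in Section 4.3 presumes a positive value, and the same nose is imaged four times. For clearance, a change within each visit, the correlation between visits is harder to guess.
- **The error is in the safe direction.** With positive correlation there are no extra false positives, the estimated differences between settings are unbiased, and the study calls itself exploratory and a pilot. That limits the harm. It does not justify fixing formal tests that discard the pairing.
- **Period.** Order is randomised, so visit effects do not bias the contrasts in expectation. A period term is standard for the design, but no size is claimed for its absence.
- **Wording.** One-way can be shorthand for a one-way repeated-measures ANOVA, and a statistical analysis plan might say so. The protocol does not, and such a plan would have to depart from its literal text.

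A reader might go further and infer that every planned p-value and interval is wrong. The protocol plans no confidence intervals, the pairwise tests may be paired, and the AUC result depends on the covariate. A reader might also infer that most of the power is lost. Against 80%, the loss is 12 points at ρ = 0.3 and 28 at ρ = 0.5; it exceeds half only near 0.7 or above.

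**Conclusion.** The models named in Section 3.4 do not fit the cross-over design, and nothing elsewhere in the protocol repairs this. The defect is the missing participant term, which leaves in the error the variation that Section 4.3 relies on removing. Its consequence for the ANOVA of T0 area and of clearance is conservatism and lost power, of the size tabulated, provided the within-participant correlation is positive. The size rests on an assumed correlation, normal data and equal correlation between visits; the pairwise figures also rest on use of the one-way error term. For the AUCs the model has the same omission, but the loss is conditional and may be small.

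**What to change.** In Section 3.4, replace the one-way ANOVA for T0 area and clearance with a cross-over model: application method as a fixed effect, participant as a random or fixed effect, and period as a standard design term. For the AUCs use the same model and keep the T0 value as covariate. Take the three pulsed-versus-continuous contrasts from that model, with small-sample degrees of freedom, and state that they are within-participant comparisons.

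The cost is a change of wording in the protocol, carried into any statistical analysis plan. The period term uses 3 degrees of freedom, leaving 27 of the 30 before any covariate. No further participants, visits or images are needed.

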### 3.0 Study objectives and endpoints

#### 3.1 Study hypothesis

It is hypothesised that increasing the pulsative frequency (0-100 Hz) produced by the NMN device will improve deposition within the sinuses.

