#### 3.2 Primary objective and endpoint

The main objective of the study is to determine the optimal frequency for the NMN that will provide the basis for future *in vivo* sinus targeting of drug delivery systems. The primary endpoint of this study is the total area of distribution (mm^2) of radiolabelled saline immediately after administration by the NMN (T0) in the different regions of the sinus cavity.

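### Pairwise tests set each pulsed setting only against continuous mode, so the stated tests cannot identify the optimal frequency or establish that deposition rises with frequency

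*Protocol*

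**What the plan says.** Protocol 3.2 states the purpose: "The main objective of the study is to determine the optimal frequency for the NMN". Protocol 3.1 states an ordered hypothesis: "It is hypothesised that increasing the pulsative frequency (0-100 Hz) produced by the NMN device will improve deposition within the sinuses".

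The analysis is in Protocol 3.4, under the heading on interpretation of quantitative data. The primary endpoint, area of distribution at T0, is "compared between treatments (A-D) which correspond to the different pulse frequencies tested". The overall test is that differences "at each subsite will be compared by means of one-way analysis of variance (ANOVA) with application method as a factor". The contrasts are then listed: "Pairwise comparisons will be performed between each of the pulsed application methods and the continuous application (no pulse". The threshold follows: "Pairwise comparisons will be tested using a two-tailed p-value of" less than 0.05. All of this is done by subsite: "This will be evaluated for each of subsites (surgically expanded ostia of the paranasal sinuses and oropharynx". The same pulsed-versus-continuous contrasts are repeated for clearance and for the retention AUCs.

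The Protocol gives no contrast between two pulsed settings, no trend or ordered contrast, and no rule for naming the optimum.

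**The concern.** The objective asks which of four settings is best. The hypothesis asks whether more frequency gives more sinus deposition. The planned contrasts ask a third question: does each pulsed setting differ from no pulsing?

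This is not detail left to a statistical analysis plan. The Protocol itself fixes the contrast set, and that set leaves out half of the possible pairs, which are the ones needed to choose between pulsed settings.

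Section 2.3 says the results will help determine deposition settings for future targeting and are intended to support registration of the device. If two or three pulsed settings beat continuous mode, the temptation is to choose the one with the smallest p-value, or to read one significant and one non-significant result as a difference between those two settings. Neither is a comparison of the settings.

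**Working it through.** **No plan figure to reproduce.** The sample size (a minimum of 10 in 5.1, 11 completers in 4.3) rests on two earlier five-person studies. No effect size, SD or power is given, so every effect below is an assumption.

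**Contrasts.** Four settings give 4 × 3 / 2 = 6 pairs. Three are planned (10, 50 and 100 Hz, each against continuous). The missing three are 10 v 50, 10 v 100 and 50 v 100 Hz.

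**Model for the illustrations.** n = 11, each participant receiving all four settings, within-participant SD = 1. Residual df are 44 − 1 − 10 (participants) − 3 (periods) − 3 (settings) = 27. For a pair differing by d, the noncentrality is d / √(2/11). This is a cross-over model; the text says one-way ANOVA, so these are not the power of the plan exactly as written.

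**Plateau: means 0 / 1.3 / 1.3 / 1.3.**
- Each planned test: 1.3 / 0.4264 = 3.05, power 84%.
- Overall F: λ = 11 × 1.2675 = 13.94, power 84%.
- By simulation, at least two planned tests are significant in about 87% of trials and all three in about 68%. No pulsed setting is better than another, and no planned test addresses that.

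**Early peak: means 0 / 1.5 / 0.75 / 0.**
- 10 Hz v continuous: 1.5 / 0.4264 = 3.52, power 92%, although the rising hypothesis is false.
- The unplanned 10 v 100 Hz comparison has the same difference, so it too would have 92% power to show the fall.

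**Rise proportional to Hz: means 0 / 0.1 / 0.5 / 1.0.**
- Trend contrast with coefficients Hz − 40, that is −40, −30, +10, +60 (sum of squares 6200): (−3 + 5 + 60) / √(6200/11) = 62 / 23.74 = 2.61, power 71%.
- Overall F: λ = 11 × 0.62 = 6.82, power 51%.
- Planned tests: 62% at 100 Hz, 20% at 50 Hz, about 6% at 10 Hz. At least one is significant in about 65% of trials.

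**The trend contrast is not better for every shape.** On the plateau its noncentrality is 1.3 × 40 / 23.74 = 2.19, power 56%, against 84% for the F test. It also rejects on a plateau more than half the time, so by itself it does not prove a continuing rise.

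**Price of covering all six pairs.** For one paired comparison with 10 df at 80% power, the detectable difference is 0.94 SD of the differences at 0.05, and 1.28 at 0.05/6 = 0.0083.

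**The case against.** Four points on the other side have force.

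**The objective and hypothesis are not wholly untested.** A reader might infer that neither is examined at all. The documents do not support that. The ANOVA covers all four settings. Continuous mode is the 0 Hz end of the hypothesised range, so the planned contrasts bear on part of 3.1. What stands is narrower: the ANOVA does not order the settings or pick one, and the contrasts never compare two pulsed settings.

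**A clear loss of power is not shown.** The advantage of a trend contrast depends on the shape assumed. In the proportional case it has 71% power against about 65% for at least one (unadjusted) planned test; on the plateau it does worse than the F test. The case rests on the question being answered, not on power.

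**Multiplicity is secondary.** A reader might infer a very large false-positive rate across subsites. The Protocol calls the study exploratory, does not count the subsites, and does not say whether the ANOVA gates the pairwise tests. Three ungated tests at one site give about 12% family-wise error; gated, about 4%. Ungated totals over several sites run from about 24% (two independent sites) to about 70% (nine), but both the count and the independence are assumptions. Nor does any rule say that a significant subsite selects the frequency.

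**More contrasts may not settle the matter.** This stands. In the proportional case, 100 Hz would separate from both 10 and 50 Hz on Tukey-adjusted intervals in only about 5% of trials. Sample size limits the answer as much as the contrast list does. That argues for reporting the uncertainty, not for leaving out the comparisons the objective needs.

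**Conclusion.** The concern holds in this limited form. As written, the tests in 3.4 can establish that pulsing differs from no pulsing. They cannot identify the optimal frequency or establish that deposition rises with frequency, because no contrast among 10, 50 and 100 Hz and no ordered contrast is planned. This conclusion follows from the text and needs no assumption.

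Its practical size does need assumptions. With 11 completers, a cross-over model and a plateau of 1.3 within-participant SD, about 87% of trials would end with two or three significant pulsed settings and no planned means of telling them apart. Other shapes and effect sizes would change that percentage. The absence of a stated adjustment is a lesser matter in an exploratory pilot and does not carry the point. The change should be made, since it needs no new data.

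**What to change.** In Protocol 3.4:

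1. Name one total-sinus endpoint as the basis for choosing a frequency. Report individual subsites descriptively.
2. From a within-participant (cross-over) model, estimate all four means and all six pairwise differences, with multiplicity-adjusted confidence intervals.
3. Keep the ANOVA, and add beside it a pre-specified ordered contrast over 0, 10, 50 and 100 Hz as the test of 3.1. Fix its spacing in advance. It should not replace the ANOVA, because it is weak on a plateau or a mid-range peak.
4. State that the setting with the highest estimated deposition is the candidate optimum, reported with its intervals against the other pulsed settings. Where an interval includes zero, describe those settings as not distinguishable.

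No extra participants, visits or imaging are needed. The cost is wider intervals: a detectable paired difference of about 1.28 instead of 0.94 SD of the differences for six Bonferroni pairs (n = 11, 80% power). With 11 completers the pulsed settings will often not be separable, and the conclusion should then say so.

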Figure 2: (A) concept of final clinical device prototype (B) cumulative aerosol particle size distribution of PARI SINUS and other commercially available nebulisers vs. the NMN prototype. Purple and blue regions correspond to optimal particle sizes for lung and nasal deposition, respectively. ( $n=5 \pm \text{StDev}$ ).

**Preliminary study:** In-line laser diffraction studies, using the development-prototype NMN (Figure 2A), have shown that a narrow particle size can be achieved which is suitable for nasal drug delivery (Figure 2B). In general, the median particle diameter of isotonic saline after 3 seconds operation was  $53.9 \mu\text{m} \pm 2.6 \mu\text{m}$ . This is in comparison to  $2.75 \mu\text{m} \pm 0.15 \mu\text{m}$  for the PARI SINUS. Under these conditions, the output rate was 20x that of the PARI SINUS. Additionally, two other commercial nebulizers were tested (Omron® and AeroNeb-Go®) and it was shown that they were also not suitable for nasal deposition (Figure 2B). Subsequently, the effect of pulsation frequency (Hz) on aerosol generation and particle size using the NMN device has been investigated and shown that changing the pulse frequency had little effect on aerosol size, measured by laser diffraction (Figure 3A).

Using a commercially available silicon cast of the human upper respiratory tract (Koken LM005, Koken Ltd, Tokyo, Japan; also referred to in this study as ‘Boris’) (Figure 3B), the effects of pulsative frequency and orifice size of the mesh on nasal deposition were evaluated.

[figure not shown]

Figure 3: (A) Influence of pulse frequency at 10 and 50 Hz on aerosol particle size over a 3-second period.  $D_{0.9}$  represents diameter of 90th percentile cumulative size distribution. ( $n=5 \pm StDev$ ). (B) Assembly (left) and testing of prototype NMN (right) in nasal cast model. Yellow water sensitive coating reacts with saline and turns red upon contact. The circled region in top view highlights the maxillary sinus inlet.

Preliminary studies using the Boris model (Figure 4) indicated these particles were deposited within the nasal cavity, with no observable oral-pharynx deposition. It also demonstrated that by applying different pulsative frequencies different nasal deposition profiles could be achieved but these observations need to be confirmed *in vivo*.

[figure not shown]

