### 2.3 Rational for current study

The proposed study aims to investigate the regional deposition in the nasal cavity of aerosols generated from the clinical NMN prototype using different pulse frequency modes. Information from this study will be used to aid in determining the optimal

deposition settings for future targeting of medication to the sinuses and within the nasal cavity.

Once beyond the nasal valve, the deposition pattern within the nasal cavity is vitally important. Deposition on middle meatus is of particular significance as this is the location of the ostiomeatal complex, a group of structures that receive drainage from the anterior and medial ethmoid cells, the frontal sinus and the maxillary sinus. Other important sites include the ostia of the sphenoid and posterior ethmoid sinuses, which are located superoposteriorly to the ostiomeatal complex on the sphenoethmoid recess and superior/supreme meatus, respectively. Improving the deposition to these regions is of clinical importance as it would translate into improved therapeutic effects in CRS, including patients that have undergone Functional Endoscopic Sinus Surgery (FESS).

To evaluate this, radio-labelled aerosols of a saline solution will be delivered using the clinical NMN prototype and sequential imaging will be performed using Single-photon emission computed tomography (SPECT) or positron emission tomography (PET) (depending on accessibility and availability of equipment in the hospital) and gamma scintigraphy imaging. Simultaneously, high resolution computed tomography (CT) scans of the nasal and sinus anatomy will be obtained from all participants and used as templates for overlaying subsequent deposition data to provide a detailed assessment of deposition characteristics.

Four different pulse frequency settings will be evaluated including: A) no pulse frequency (continuous delivery mode), B) a 10 Hz pulse frequency C) a 50 Hz pulse frequency and D) a 100 Hz pulse frequency based on preliminary *in vitro* studies and those investigated by other researchers [9].

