### 3.4 Data analysis and interpretation

Defined volume of radiolabelled saline (2 ml) will be delivered using the NMN device through the nasal airways with four different pulse frequency settings in front of a single-head gamma camera using the NMN device to capture a planar images. Subsequently, serial images (2 frames per second) will be recorded from the anterior and lateral view using the SPECT/CT. This allows dynamic studies of filling and emptying of the nose, including the sinuses.

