#### 6.3.1 Radiolabel and radiation dose

An isotonic saline solution (0.9% w/v) will be mixed and delivered together with the technetium labelled diethylene triamine pentaacetic acid ( $^{99m}\text{Tc}$ -DTPA). DTPA is a nano-colloid of 492 Dalton size. In nuclear medicine, DTPA aerosols are used for ventilation imaging and for measurement of alveolar transmembrane permeability.  $^{99m}\text{Tc}$ -DTPA is cleared from the lungs into the circulation by passive diffusion through the paracellular junctions of the alveolar capillary barrier with a half-life of approximately 70 minutes in a healthy non-smoker participant [9, 24, 25]. DTPA was selected due to its saline solubility and the ability to easily measure clearance either through mucociliary or absorption through the sinuses and nasal cavity.

Technetium will be provided by the radiopharmacy department at the Royal North Shore Hospital. A solution of  $^{99m}\text{Tc}$ -DTPA will be prepared immediately before administration using a commercially available kit (TechneScan DTPA; Mallinckrodt Medical BV). A total of 2 mL of saline  $^{99m}\text{Tc}$ -DTPA (approximately 0.24 mSv) will be added to the device drug reservoir of the NMN prototype.

Each 2mL dose contains a radiolabeled saline solution which equates to a radiation dose of approximately 0.24 mSv.

During the first visit participants are subjected to a high-resolution head CT scan which equates to a radiation dose of 1.9 mSv. Therefore, the total radiation dose that each participant would be exposed to is estimated to be up to 2.86 mSv. This calculated radiation exposure is classified as low as it is markedly lower than the dose constraint of 5 mSv/year, it is therefore within the acceptable limits as per the ARPANSA Code of Practice *Exposure of Humans to Ionizing Radiation for Research Purposes* 2005 [19].

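### Clearance and retention are tested at the sinus ostia and oropharynx, where the net change mixes inflow with outflow and can, over some intervals, misrank the pulse settings

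*Protocol*

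**What the plan says.** All references are to the protocol.

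- **Definition of clearance (3.4, Interpretation and assumption of quantitative data):** "Clearance will be calculated by the decrement in total radiolabelled saline between" time zero, 20 and 60 minutes. Counts are corrected for background and radioactive decay, and for nothing else.
- **Where it is tested (same section):** "Clearance will be evaluated for each subsite and compared between treatments (A-D", by one-way ANOVA with pairwise comparisons against continuous delivery.
- **Retention (3.4):** AUC from 0 to 60 minutes of area and of intensity. "The AUCs will be evaluated for each subsite and compared between treatments (A-D". The test is an ANCOVA with the time-zero value as covariate.
- **What a subsite is:** the only definition comes with the primary endpoint: "This will be evaluated for each of subsites (surgically expanded ostia of the paranasal sinuses and oropharynx".
- **Different regions in the same section:** its opening paragraph sets deposition, retention and clearance as a percentage of total nasal deposition, in the nasal cavity and the left and right maxillary, frontal, ethmoidal and sphenoidal sinuses.
- **Movement of tracer:** section 2.3 describes the ostiomeatal complex as "a group of structures that receive drainage from the anterior and medial ethmoid cells, the frontal sinus and the maxillary sinus". Section 6.3.1 says the label was chosen for "the ability to easily measure clearance either through mucociliary or absorption through the sinuses and nasal cavity". Section 3.4 says of the serial images: "This allows dynamic studies of filling and emptying of the nose, including the sinuses".
- **Oropharynx at delivery:** section 2.2 reports for the nasal cast that particles deposited in the nasal cavity "with no observable oral-pharynx deposition".
- **Population:** section 5.3.2 excludes anyone with a history of upper-airway surgery, the nasal cavity in particular.

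**The concern.** A fall in activity equals clearance only where nothing arrives after time zero. Sinus drainage passes through the ostial region, as section 2.3 says. Mucociliary transport moves label from one site to another. The protocol does not say outright that it reaches the oropharynx, but this follows from that route and from the oropharynx lying downstream of the nose. At both sites the measured fall is therefore outflow minus inflow, and the AUC counts arriving tracer as retained tracer.

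A setting that clears the nose faster can then appear to clear the oropharynx less. A setting that loads the sinuses better, which is what the study hypothesis in section 3.1 expects, can appear to clear the ostia more slowly. The second secondary objective in section 3.3, clearance of the labelled saline over one hour, is not measured by either quantity.

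**Working it through.** The protocol states no clearance figure or transport rate, so there is nothing to reproduce. The check asks whether the per-subsite measure follows true clearance in a simple linear drainage model. All rates and loads below are assumptions; only the times 0, 20 and 60 minutes come from the protocol.

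**1. Oropharynx fed by the nose.** Nose at time zero 100 units, oropharynx 0, swallowing rate 0.2/min, nasal clearance rate k.

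P(t) = 100 × k/(0.2 − k) × [exp(−kt) − exp(−0.2t)]

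For k = 0.01 at 20 min: 100 × 0.01/0.19 × (0.8187 − 0.0183) = 4.21.

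| k per min | P(20) | P(60) | Fall 0-20 | Fall 0-60 | Fall 20-60 | AUC 0-60 |
|---|---|---|---|---|---|---|
| 0.01 | 4.21 | 2.89 | -4.2 | -2.9 | 1.3 | 211 |
| 0.02 | 7.24 | 3.35 | -7.2 | -3.3 | 3.9 | 333 |
| 0.04 | 10.78 | 2.27 | -10.8 | -2.3 | 8.5 | 443 |

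The AUC is the integral of P: 100 × k/(0.2 − k) × [(1 − exp(−60k))/k − (1 − exp(−12))/0.2].

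The ranking is backwards for 0-20 min and for the AUC. It is not backwards elsewhere: at 0-60 min the order is mixed and the fastest setting ranks best, and at 20-60 min the order is correct.

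**2. Ostia fed by a sinus.** Ostia at time zero 20 units, ostial drain rate 0.05/min and sinus drain rate 0.02/min in both settings, sinus load S of 5 or 15 units.

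O(t) = 20 exp(−0.05t) + S × 0.02/0.03 × [exp(−0.02t) − exp(−0.05t)]

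- S = 5: O(20) = 7.358 + 3.333 × 0.3024 = 8.37; O(60) = 1.83. Apparent clearance is (20 − 8.37)/20 = 58% and (20 − 1.83)/20 = 91%.
- S = 15: O(20) = 7.358 + 10 × 0.3024 = 10.38; O(60) = 3.51. Apparent clearance is 48% and 82%.

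The true ostial rate and the time-zero value are the same in both settings, so neither scaling to time zero nor the ANCOVA covariate can remove the difference. The absolute 20-60 min fall is 6.53 against 6.87, so on that interval the higher load does not look slower.

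**3. All compartments together.** Sinus to ostia to nasal cavity to oropharynx to swallowed, with the same time-zero split in both settings: 6.5, 5, 86.5 and 2% of dose. The 6.5 borrows the comparator's sinus share from the Statistical consideration paragraph; the rest is assumed. Half-lives are 120 min (sinus) and 60 min (nose) for a slow setting, 40 and 15 min for a fast one, and 20 min for ostia and oropharynx in both.

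| Measure | Slow | Fast |
|---|---|---|
| True loss from the whole system, 0-60 | 29.7 | 64.0 |
| Oropharynx fall, 0-20 / 0-60 | -12.0 / -15.4 | -35.6 / -22.2 |
| Oropharynx AUC | 857 | 1845 |
| Ostia fall, 0-20 / 0-60 | 2.0 / 3.6 | 1.2 / 2.9 |
| Ostia AUC | 159 | 205 |
| Sinus fall, 0-60 | 1.9 | 4.2 |
| Sinus + ostia + nasal cavity fall, 0-60 | 1.9 + 3.6 + 39.6 = 45.1 | 4.2 + 2.9 + 79.1 = 86.2 |

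Here the faster setting looks worse at both subsites, while the sinus region and the summed region rank it correctly.

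**The case against.** **The reversal depends on interval and assumptions.** This stands. In the first model only the 0-20 min fall and the AUC are reversed. The second holds ostial time-zero activity equal while tripling the sinus load. The third lets upstream rates differ while local rates stay equal; if local rates also differ, reversal is not certain. The first and third need pulse frequency to alter the nasal clearance rate, whereas section 3.1 hypothesises only an effect on sinus deposition. A reader might infer that the clearance comparisons will come out backwards. The protocol gives no rates to support that.

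**Near-zero oropharyngeal activity at delivery is not established.** This also stands. The cast volume given with Figure 4 is 0.33 mL, and the trial delivers 2 mL, about six times as much (2/0.33 = 6.1). A reader might infer that the oropharyngeal fall can never be positive; that holds only if activity there starts near zero. The inflow problem itself does not need a zero start.

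**The ostial subsite cannot exist here, so the subsite definition is the real defect.** This is partly right. Surgically widened ostia cannot occur in volunteers excluded for nasal surgery, and the opening of the same section names other regions. But the tests are worded for each subsite, and that term has no other definition. Even if it was meant to include the sinuses and nasal cavity, the oropharynx would still be tested.

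**These are secondary endpoints in an exploratory pilot, and a subsite AUC validly describes local exposure.** Both points are true. They limit the consequence but do not turn local exposure into retention of what was deposited there.

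**Conclusion.** The point holds in a limited form. Section 3.4 fixes the clearance and retention tests at sites that can be fed from upstream and makes no allowance for inflow, so the results there do not measure the clearance sought in section 3.3. For some intervals they can rank the settings in the wrong direction. How large or how frequent that would be is unknown, because every rate used here is assumed.

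It would be wrong to infer that the primary comparison or the choice of frequency is invalidated: the primary endpoint is area at time zero and is untouched. The wording should be corrected because the definition also conflicts with the regions listed at the start of the same section and with the surgical exclusion in section 5.3.2.

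**What to change.** In section 3.4:

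1. Run the clearance and AUC tests on regions the section already lists: the summed nasal cavity plus all sinuses and, separately, the pooled sinuses. Express each as a percentage of total nasal deposition at time zero.
2. Remove the ostia and oropharynx from the clearance and retention tests. Report them as descriptive time-activity curves, and label oropharyngeal change after time zero as net transit.
3. Reconcile the subsite definition with the opening paragraph of that section and with section 5.3.2.

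The change is to wording only, with the same images and regions. The costs are these:

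- There are fewer subsite tests.
- The nasal cavity dominates the summed region (the comparator had about 6.5% in the sinuses), so that result says little about the sinuses.
- The pooled sinuses may still fill after time zero, so the two results must be read together.
- On a total-deposition scale a heavier sinus load gives a larger sinus fall at the same rate: loads of 2 and 20 with a 60-minute half-life fall by 1.0 and 10.0 in an hour, 50% each. The sinus value at time zero should therefore be shown alongside.
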